14.5.2 Secondary efficacy variable

The secondary endpoints are time to improvement of at least 2 points on the WHO Ordinal Scale, the proportion of subjects with ARDS (defined by Berlin severity criteria) within 14 days after enrollment and the proportion of participants alive and not having required invasive or non-invasive ventilation at 14 days after enrollment. They will be tested only after a significant test of the primary endpoint (a priori ordered hypotheses), therefore, no alpha adjustment is necessary.

Quantitative secondary study parameters will be described based on their mean, standard deviation, median, IQR, minimums and maximums and portrayed by Kaplan-Meier plots and compared with the Wilcoxon rank test.

	Trial Substance:	Ruconest®	Study No.: C1 6201 PROTECT-COVID-19-US
	Short Title:	Ruconest®: Prevention of severe SARS-CoV-2 infection in hospitalized patients with COVID-19	Sponsor: Pharming Technologies B. V.

Qualitative secondary study parameters will be analyzed by means of absolute and relative frequencies. Pairwise Chi-Square tests will be carried out in order to compare each of the active treatments to placebo. Moreover, 95% confidence intervals for the treatment differences will be calculated.

Other outcomes of interest will be analyzed by means of descriptive and exploratory statistics. The analyses will be carried out by the trial biostatistician.

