Statistical Considerations:	
Detailed methodology for statistical analyses of the data collected in this trial will be documented in a Statistical Analysis Plan.
 
Full Analysis Set/Intent-to-Treat Population: The FAS/ITT Population is defined as all patients who are randomly allocated to a study arm. Statistical analyses will be based on the treatment arm to which the patient was allocated.
 
Safety Population: The Safety Population is defined as all patients who received at least one dose of rhC1INH.
 
The primary endpoint WHO 7-point outcome scale at day 7 will be analyzed by means of the nonparametric Wilcoxon rank test stratified by its baseline values with two-sided α-level of 5 %.
 
The secondary endpoint is time to improvement of at least 2 points. It will be tested only after a significant test of the primary endpoint (a priori ordered hypotheses), therefore, no alpha adjustment is necessary.
 
Furthermore, 95% confidence intervals will be determined, and the results will be presented graphically by means of box-and-whisker plots.
 
Time to event (e.g. death, virological clearance, defervescence) will be displayed by Kaplan-Meier plots and compared with a Wilcoxon rank test. Appropriate statistical tests will be used for the analysis of other outcomes of interest and will be detailed in the statistical analysis plan prior to unlocking of the study database.

GCP Statement:	This study will be conducted in compliance with the protocol, the Sponsor's standard operating procedures and/or guidelines, the United States Food and Drug Administration (FDA) regulations, the current version of the Declaration of Helsinki, the International Conference on Harmonization (ICH) GCP guidelines and other local regulations, as applicable.
-----------------------	---

ABBREVIATIONS

Provide a list of abbreviations used on the protocol - to be completed

AE	Adverse Event
ALI	Acute lung injury
C1-INH	C1 inhibitor, C1 esterase inhibitor
COVID-19	Coronavirus disease 2019
CRF	Case Report Form (Paper)
CS	Complement system
CTCAE	Common terminology criteria for adverse events
DSUR	Drug safety update report
EMA	European Medicines Agency
FDA	Food and Drug Administration
GCP	Good Clinical Practice
HAE	Hereditary Angioedema
Ho	Null hypothesis
H1	Alternative hypothesis
HRI	Host-Related Impurities
IB	Investigator's Brochure
IC	Informed Consent
ICU	Intensive Care Unit
IME	Important Medical Event
IMP	Investigational Medicinal Product

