5.2 Secondary Outcomes

The secondary endpoints will evaluate the effect of rhC1INH treatment in addition to SOC treatment relative to only SOC treatment on disease progression as measured by

- Time to clinical improvement (time from randomization to an improvement of two points on the seven-category WHO Ordinal Scale or live discharge from hospital, whichever came first) within 14 days after enrollment.
- Proportion of participants alive and not having required invasive or non-invasive ventilation at 14 days after enrollment.
- Number of days hospitalized (per patient)
- Number of days alive (per patient)

- Proportion of subjects with ARDS (defined by Berlin severity criteria) within 14 days after enrollment

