6. STUDY DESIGN

6.1 General Study Design and Justification of Design

This is an exploratory, randomized, parallel-group, open-label, multi-center, phase 2 clinical study in patients with confirmed COVID-19 infection and admitted to the hospital for treatment of SARS-CoV-2 infection to estimate the effect size of rhC1INH treatment compared to SOC on the proportion of patients surviving without requiring mechanical ventilation.

The study will recruit approximately 120 patients (80 patients in the intervention and 40 in the control arm) from approximately five to ten sites in the United States. Sites will be selected on the basis of estimated numbers of cases, the availability of a committed principal site Investigator and research team, and the capacity to collect samples as per protocol.

Participants will be randomly assigned in a 2:1 ratio to rhC1INH treatment in addition to standard of care (SOC) or SOC stratified by the site. Screening, informed consent and randomization will happen as early as possible after admission to the hospital, usually within 48 hours after admission. Participants will receive intravenous rhC1INH in addition to standard of care (SOC) or SOC during an admission period starting on the day after informed consent (=day 0). Both groups will continue to receive SOC treatment for COVID-19 infection. Blood samples will be collected before and during the 4-day period of treatment. Follow-up will include the period until discharge and a weekly telemedicine interview or telephone call for 3 months post treatment to assess potential adverse events and outcomes.

Duration of participant's participation will be approximately 14 weeks (+/- 5 days). Screening phase duration is up to 48 hours; intervention period is 14 days (including a treatment phase of 4 days) and follow-up period of 3 months starting post-treatment on Day 0. After discharge, follow-up information is obtained on a weekly basis until 3 months post-treatment. When no response is received within 5 weeks following discharge the participant may be considered as lost to follow-up.

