9.1.2 Assessment of Secondary Outcomes

- For the analysis of time to clinical improvement of at least 2 points in the WHO Ordinal Scale for Clinical Improvement, clinical severity will be assessed every day until day 14 according to the Scale with the worst status for that day recorded.
- For the analysis of the proportion of patients alive and not having required invasive or non-invasive ventilation at 14 days after enrollment, admission to ICU with invasive or non-invasive ventilation or death will be assessed every day until day 14.
- For the analysis of the proportion of patients with ALI within 14 days after enrollment, PaO₂/FiO₂ will be determined daily until day 14. This is only relevant for patients with arterial blood gas sampling performed in the ICU or rarely in the medical unit.

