14.5 Efficacy

Continuous variables will be summarized using the mean, standard deviation, median, minimum, maximum values. Categorical variables will be summarized using the cell frequencies and percentage of patients in each category.

All statistical tests performed will be two-tailed with significance determined by reference to the 5 % significance level, unless otherwise stated. The null hypothesis at all times will be the equality of the treatments being compared.

Furthermore, the results will be presented graphically.

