14.8 Multiplicity

Pocock's group sequential approach is used and the significance levels in the interim analysis are adjusted for the primary variable accordingly ($\alpha_p = 0.0221$).

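### Three secondary endpoints are tested at 5% with a significant primary as the only written condition; no stop rule among them is written to support the statement that alpha needs no adjustment

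*SAP*

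**What the plan says.** SAP 14.5.2 lists time to improvement of at least two points, ARDS within 14 days, and being alive without ventilation at 14 days. It then states: "They will be tested only after a significant test of the primary endpoint (a priori ordered hypotheses), therefore, no alpha adjustment is necessary". Protocol 11.4.3 has the same three endpoints, order and sentence.

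The protocol synopsis (Statistical Considerations) has only one secondary at this place: "The secondary endpoint is time to improvement of at least 2 points". It draws the same conclusion: "It will be tested only after a significant test of the primary endpoint (a priori ordered hypotheses), therefore, no alpha adjustment is necessary".

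The level comes from SAP 14.5: "All statistical tests performed will be two-tailed with significance determined by reference to the 5 % significance level, unless otherwise stated". No section gives another level for a secondary. SAP 14.8, the multiplicity section, deals with the primary only: "the significance levels in the interim analysis are adjusted for the primary variable accordingly".

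The outcome lists use a different order. The synopsis (objectives and outcomes), Protocol 4.3 and 5.2, and SAP 4 and 5.1.2 all put alive without ventilation before ARDS. Protocol 5.2 and SAP 5.1.2 also add two outcomes that the analysis sections do not name among the tested secondaries: "Number of days hospitalized (per patient") and the number of days alive.

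**The concern.** A significant primary protects the step from the primary to the secondaries. It does not protect three secondaries from one another. Once that gate opens, three tests at 5% each offer three chances of a false result. Leaving the level alone is justified if there is one secondary, or if each secondary is tested only when the one before it succeeded. Neither is written for the three.

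What is at stake is the labelling of results. Suppose the primary succeeds, time to improvement does not, and the ventilation endpoint gives p = 0.03. One analyst, applying the written condition, calls the ventilation result significant. Another, reading the ordering as a strict sequence, calls it descriptive. The trial is open-label (Protocol 6.2.2) and the SAP is to be finalized only after the blind review (SAP 1), so the question could be settled late.

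**Working it through.** **The plan's own figure.** The only multiplicity figure is the Pocock level 0.0221. Three equally spaced looks at overall two-sided 5% give 0.02205, which is 0.0221 to four decimals, so it reproduces. It concerns the primary only.

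**Inputs from the documents.** Three secondaries (SAP 14.5.2); two-sided 5% each (SAP 14.5), so |Z| > 1.96; primary at two-sided 0.0221 per look, so |Z| > 2.289; planned power 80% (SAP 6). The SAP puts the looks at 40, 80 and 120 patients, the protocol at 32, 80 and 120. Both were run.

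**Assumptions.** The four test statistics are normal with one common correlation, which the documents do not give. Increments between looks are independent and weighted by patient numbers. The secondaries are tested once, at the look where the primary crosses. The primary's expected Z at 120 patients is 3.05, giving power of about 81%. Time to improvement has an effect of the same strength; ARDS and alive without ventilation have none. There were 600,000 simulated trials per cell.

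**Hand check at correlation 0.** Two null tests give 1 - 0.95² = 0.0975 once the gate is open. Times the chance that it opens: 0.81 × 0.0975 = 0.079. With a stop rule, a false claim needs time to improvement to be claimed first (0.51 in the simulation) and then the second endpoint to be falsely rejected: 0.51 × 0.05 = 0.0255. Both agree with the simulation.

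**Chance of at least one false secondary rejection, either direction, primary power about 81%:**

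| Correlation | As written, 40/80/120 | As written, 32/80/120 | Stop rule, 40/80/120 | Stop rule, 32/80/120 |
|---|---|---|---|---|
| 0 | 7.9% | 7.9% | 2.6% | 2.6% |
| 0.3 | 7.4% | 7.4% | 2.9% | 2.9% |
| 0.5 | 6.6% | 6.7% | 3.1% | 3.1% |
| 0.7 | 5.5% | 5.8% | 3.0% | 3.2% |
| 0.8 | 4.7% | 5.2% | 2.9% | 3.2% |
| 0.9 | 4.0% | 4.4% | 2.9% | 3.1% |

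**Primary power near 1** (expected Z of 5, power 99.7%), as written: 9.7% at correlation 0, 7.1-7.3% at 0.7 and 5.5-5.6% at 0.9.

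**Benefit only, power about 81%.** False claims of benefit occur in 4.0-5.5% of trials over correlations 0 to 0.9, against 2.0-3.2% for a single null secondary behind the same gate.

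**Which order.** In this model ARDS and alive without ventilation are interchangeable, so the stop-rule columns hold for either order of the two. The order matters for what can be claimed: under a stop rule the third endpoint can be claimed only if the second succeeds.

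**The case against.** The best reply is that hypotheses ordered in advance already mean a fixed sequence, since only a sequence with dependent steps would justify leaving the level alone. That reading is possible. It would make the sentence correct and leave only an operating rule to write down. But the synopsis uses the same parenthesis for a single secondary, where it can only mean primary first and secondary second. So the phrase alone does not order the three, and nothing says that testing stops.

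A second reply is that the size is modest. That stands. ARDS and ventilation are likely to be strongly correlated, because Protocol 9.1.2 says of the blood-gas assessment: "This is only relevant for patients with arterial blood gas sampling performed in the ICU or rarely in the medical unit". At a correlation of 0.8 to 0.9 and about 81% power, the error is near or below 5% without any stop rule. Section 9.1.2 supports high correlation for that pair only, however, not across all four endpoints as the common-correlation model has it.

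A third reply is the trial's purpose. Protocol 6.1 says: "This is an exploratory, randomized, parallel-group, open-label, multi-center, phase 2 clinical study". Strict control among secondaries is partly a matter of choice in such a trial. The plan nevertheless makes a formal statement about alpha, and the written rule does not support it.

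A reader might go further and infer that three unadjusted tests will certainly be run, with a false-positive rate of 1 - 0.95³ = 14.3%. The documents do not support that. They leave the rule unwritten; they do not exclude a sequence. The 14.3% also needs independent endpoints, a primary certain to succeed, and no effect on time to improvement. The last is hard to believe beside a real primary effect, because that endpoint is largely a gain on the primary's own scale.

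**Conclusion.** The point holds as a gap in the written rule. Three secondaries at two-sided 5%, with a significant primary as the only written condition, do not justify the conclusion that alpha can be left alone; one secondary would, and so would a sequence with a stop.

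As written, the chance of at least one false secondary rejection is about 8% at correlation 0, 5.5-6% at 0.7 and 4-4.5% at 0.9, and up to about 10% if the primary's power is near 1. With a stop rule at 81% power it is about 3%. These figures rest on assumed correlations and on time to improvement being truly affected while the other two are null.

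It would be wrong to infer that the primary result is compromised. Its type I error, the sample size and the stopping rules do not depend on how the secondaries are tested. The consequence is limited to which secondary results may be called significant. It should be corrected, and the correction is small.

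**What to change.** Before any comparative result is seen:

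- State one test order explicitly in SAP 14.5.2 and 14.8 and in Protocol 11.4.3. The order in the two analysis sections (time to improvement, ARDS, alive without ventilation) is the natural default. The sponsor must confirm it, because the objective and outcome lists put alive without ventilation before ARDS.
- Add a sentence such as: *Each secondary endpoint is tested at two-sided 5% only if the previous one is significant; testing stops at the first non-significant result, and later endpoints are then descriptive.*
- Align the synopsis with the chosen rule, and label days hospitalized and days alive as descriptive in Protocol 5.2 and SAP 5.1.2.

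Holm's procedure across the three is the alternative. It is itself an adjustment, so the statement that none is needed would have to go.

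The cost is a few lines of text, with no change to data or sample size. The stop rule's drawback is that a lower-ranked endpoint cannot be claimed if an earlier one fails. Holm avoids this but loses power on the first endpoint. If time to improvement has an effect as strong as the primary's, the chance of claiming it is 51-76% with the stop rule and 39-62% with Holm (correlations 0 to 0.9, looks at 40/80/120, primary power about 81%).

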6.2.1 Randomization

Participants will be randomized to two parallel groups in a 2:1 ratio to receive either rhC1INH (intervention) in addition to standard of care (SOC) or SOC treatment (control). Randomization will be stratified by the study site before inclusion using randomly permuted block sizes of four.

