6 SAMPLE SIZE

This is a pilot study investigating the efficacy and safety of rhC1-INH in the prevention of clinical deterioration in a high-risk population with COVID-19. There is no reliable information available on the clinical evolution of the population included in the trial. Therefore, a precise quantitative pre-definition of the sample size of a population needed to obtain clinically significant primary endpoint is not possible at this point in time.

The assumptions which are proposed and the criteria to monitor and assess the primary endpoint are as follows:

The primary endpoint is a 7-point scale and the standard deviation σ can be expected as 1.5 points. A relevant effect δ is an advantage of at least 1 point. Then, the standardized difference is about $\delta/\sigma = 0.67$. For a fixed sample size design with a two-sided significance level of $\alpha = 0.05$ and a power of $1 - \beta = 0.80$, a sample size of $N = 2 \times 38$ is necessary. Because of a nonparametric test, we add 4 patients in each group, and because of drop-outs we add also 4 patients in each group to $N = 2 \times 46$. For a 2:1-randomization, a nonparametric analysis by the stratified Wilcoxon rank-test, and an adaptive group sequential analysis, the overall sample size is estimated as $120 = 80 + 40$.

All patients are hospitalized, and it is very unlikely that the primary endpoint at Day 7 will not be measured. Nevertheless, a drop-out rate of about 10% is included.

Adaptive design:

Two interim analyses after 40 and 80 patients are planned according to the Pocock adjusted levels $\alpha_p = 0.0221$. Based on the results of an interim analysis the sample size can be adjusted (Lehmacher, Wassmer, 1999). There are no prespecified futility margins, but the DSMB can recommend stopping the study in the case of insufficient interim results.

The primary efficacy endpoint and the main secondary efficacy endpoints will be analyzed at latest at 14 days after start of treatment.

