14.5.1 Primary efficacy variable

The primary endpoint WHO Ordinal Scale measure at day 7 will be analyzed by means of the nonparametric Wilcoxon rank test stratified by its baseline values with two-sided α -level of 5%. Two adaptive interim analyses after 40 and 80 patients are planned according to the Pocock adjusted levels $\alpha_p = 0.0221$. The results of the sequential groups are combined by the inverse-normal-method (Lehmacher, Wassmer, 1999). There are no prespecified futility margins, but the DSMB can stop the study in the case of insufficient interim results.

Furthermore, 95% confidence intervals will be determined, and the results will be presented graphically by means of box-and-whisker plots.

The analyses will be carried out by the trial biostatistician.

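### The gated secondary tests are not stratified by baseline WHO score although the primary test is; the cost is some precision, not validity

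*SAP*

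**What the plan says.** SAP 14.5.1 and protocol 11.4.2 analyse the Day 7 WHO score by a "nonparametric Wilcoxon rank test stratified by its baseline values".

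SAP 14.5.2 and protocol 11.4.3 then name three secondary endpoints to be tested once the primary is significant: time to a 2-point improvement, the proportion with ARDS by Day 14, and the proportion alive without ventilation at Day 14. Quantitative endpoints are to be "portrayed by Kaplan-Meier plots and compared with the Wilcoxon rank test". For proportions, "Pairwise Chi-Square tests will be carried out in order to compare each of the active treatments to placebo", with 95% confidence intervals for the treatment differences. Neither sentence names a stratum or covariate. SAP 14.5 makes all efficacy tests two-sided at 5% unless otherwise stated.

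Baseline WHO score is assessed on Day 0 (protocol 9.1 and 9.2.1). On allocation, protocol 6.2.1 says "Randomization will be stratified by the study site before inclusion"; baseline severity is not a factor. The synopsis hypothesis concerns patients at scores 3 or 4, but the eligibility criteria in protocol 7.1 exempt high-flow oxygen from the ventilation exclusion, and protocol 5.1 scores high-flow oxygen as 5.

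**The concern.** The sponsor treats baseline WHO score as important enough to stratify the primary test, then does not carry it into the tests that follow in the hierarchy. With 40 controls, the arms can differ by chance in baseline severity, and an unstratified comparison leaves that variation in the error term. What is at stake is the precision of the secondary results.

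Time to improvement has a further problem, because baseline score partly defines the event. An unstratified test pools patients who can meet the endpoint in different ways.

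The chi-square sentence also describes a different trial: it refers to several active treatments and a placebo, whereas this trial has one active arm and an SOC control. It has to be rewritten in any case.

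**Working it through.** **The plan's own figure.** The only sample-size figure is for the primary endpoint: 1 point, SD 1.5, two-sided 5%, 80% power, 38 per arm. The normal formula 2(1.96 + 0.84)²/(1/1.5)² gives 35.3, so 36; the t-test version gives 37. The total follows from 92 × 9/8 (2:1 allocation) = 103.5, times a three-look Pocock inflation of 1.166 for equally spaced looks = 120.7, against 120 stated. The figure reproduces, and this point does not affect it. No power is stated for any secondary endpoint.

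**Power of the planned chi-square.** Protocol 3.8 says 15-20% of hospitalised patients progress to mechanical ventilation and ICU support; I take this as the control event rate. With 80 versus 40,

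power = Φ[(|pC − pT| − 1.96·SE₀)/SE₁], with SE₀ pooled and SE₁ unpooled.

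For 20% versus 10%: SE₀ = √(0.1333 × 0.8667 × 0.0375) = 0.0658 and SE₁ = √(0.16/40 + 0.09/80) = 0.0716, so power = Φ(−0.405) = 34%. Over control rates of 15-20%, power is 27-34% for a halving of risk and 58-70% for a 75% reduction. At an assumed 30%, since the endpoint also counts non-invasive ventilation and death, it is 49% and 87%.

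**What stratification adds.** Under the null, the crude risk difference has variance p(1 − p)(1/80 + 1/40). The stratified one has approximately Σ wₖpₖ(1 − pₖ)(1/80 + 1/40), where wₖ is the share at score k. For shares 25/55/20% at scores 3/4/5 with risks 5/15/45%: p = 0.185, p(1 − p) = 0.1508, and the within-stratum sum is 0.0119 + 0.0701 + 0.0495 = 0.1315. The SDs are √(0.1508 × 0.0375) = 7.5 points and √(0.1315 × 0.0375) = 7.0 points, a variance ratio of 1.15. In simulation of this case, power at OR 0.3 rises from 46% to 49%.

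The table gives the same ratio for other assumed mixes, with power from 40,000 simulated trials per scenario (80 versus 40, two-sided 5%, chi-square → Cochran-Mantel-Haenszel):

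| Scores and shares | Control risks | Variance ratio | Power, OR 0.5 | Power, OR 0.25 |
|---|---|---|---|---|
| 3/4: 30/70% | 12/22% | 1.01 | 25.7 → 26.1% | 61.4 → 62.4% |
| 3/4: 10/90% | 5/21.7% | 1.02 | 26.2 → 26.8% | 63.6 → 64.6% |
| 3/4: 30/70% | 5/25.5% | 1.06 | 24.8 → 25.6% | 60.8 → 62.9% |
| 3/4/5: 20/65/15% | 5/17/53% | 1.15 | 22.5 → 24.2% | 57.3 → 60.9% |
| 3/4/5: 25/50/25% | 2/10/58% | 1.44 | 17.4 → 21.2% | 48.2 → 56.4% |

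At OR 1 both tests reject in about 5% of trials in every scenario. Shares, risks and odds ratios are assumptions; the documents give none.

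**Chance imbalance.** With 20% at score 5, the arm difference in that share has SD √(0.2 × 0.8 × 0.0375) = 7.7 points. The risk gap in the 25/55/20% example is 45% minus (0.25 × 5% + 0.55 × 15%)/0.80 = 11.9%, or 33 points. An imbalance of one SD moves the crude difference by about 7.7 × 0.33 = 2.5 points. This is already part of the 7.5-point SD above, not an addition to it.

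**Time to improvement.** The event is a 2-point gain or live discharge, whichever is first (protocol 5.2). From 3 the gain means reaching 1, and from 4 reaching 2; both are outpatient states, so for both groups the event is in effect live discharge. From 5 it means reaching 3, still in hospital but without oxygen. Only score 5 differs.

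**The case against.** The case for leaving the plan alone is substantial. This is an exploratory pilot, the endpoints are gated, and no power is claimed for them. The planned chi-square keeps its type I error. If enrolment matches the synopsis hypothesis of scores 3 and 4, stratification is worth 2 points of power at most. The larger gains need an assumed sizeable share at score 5, and the exclusion of patients in or about to enter the ICU may keep that share small. All of this stands, and it limits the size of the point.

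It can also be said that the documents are silent rather than unadjusted. That is literally true, but a plain chi-square has no strata, and the primary section says so when stratification is meant. If the intention is open, it should be settled now: the trial is open-label, and SAP section 1 finalises the plan only after data review.

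Site, the one factor stratified at randomisation, is also absent from the secondary tests. But it is absent from the primary test too, so it is a separate question.

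Some stronger readings are tempting, and the documents do not support them:

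- A reader might infer that baseline WHO score is the strongest recorded predictor of ventilation and ARDS. Protocol 7.1 lists eight risk factors for ventilation, does not rank them, and does not include the WHO score.
- A reader might infer that chance imbalance biases or invalidates the planned tests. Their variance already allows for it.
- A reader might infer that primary and secondary results would answer different questions. A risk difference is collapsible, so if it is similar across strata the crude and Mantel-Haenszel estimates target the same quantity.
- A reader might infer that each baseline score sets its own improvement target. That overlooks the live-discharge component.

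**Conclusion.** The point holds as a modest, free gain in precision. A baseline measure that is already collected and already stratifies the primary test is not used in the gated secondary tests, in either document. The planned tests are valid. For a ventilation-type proportion with about 20% control events, stratifying adds about 0.4 to 2 points of power with scores 3 and 4 only, and about 2 to 8 points if score 5 is common and strongly prognostic. These figures rest on assumed mixes and risks, and no loss was quantified for ARDS or time to improvement. To say that the plan throws away decisive information would overstate this: at 20% there are about 24 events in 120 patients, and that is the main limit. For time to improvement the argument rests on the definition: score 5 patients can meet the event in hospital, and the others in effect cannot.

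**What to change.** In SAP 14.5.2 and protocol 11.4.3, before the data review:

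- For the ARDS and ventilation-free proportions, replace the chi-square test with a Cochran-Mantel-Haenszel test stratified by baseline WHO score, and report a Mantel-Haenszel risk difference with its 95% CI.
- Stratify the time-to-improvement test by the same factor.
- Correct the comparison to rhC1INH plus SOC versus SOC.
- If the sponsor prefers unstratified secondary tests, say so and give the reason for departing from the primary analysis.

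The cost is wording in two documents and a changed procedure call. Data collection and sample size are unaffected.
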